## 13.0 ADVERSE EVENT REPORTING REQUIREMENTS

### 13.1 Definitions

#### 13.1.1 Adverse Event (AE)

An adverse event (AE) is any undesirable sign, symptom or medical condition or experience that develops or worsens in severity after starting the first dose of study treatment or any procedure specified in the protocol, even if the event is not considered to be related to the study.

Abnormal laboratory values or diagnostic test results constitute adverse events only if they induce clinical signs or symptoms or require treatment or further diagnostic tests.

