#### 7.1.2 Adverse Event List(s) for Carboplatin

The major dose limiting toxicities observed with Carboplatin single agent are myelosuppression and renal toxicity.

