#### **Dose Modification for Thrombocytopenia**

Nadir of last course ≤ 100,000	Dose of Cisplatin Platelets (day 1 of each cycle)	
	<100,000	≥100,000
≥ 50,000	Hold	Cisplatin = 100%
< 50,000 (1 st occurrence)	Hold	Cisplatin = 80%
<50,000 (2 nd occurrence)	Hold	Cisplatin = 60%

\*\* Please note that dose reduction percentage is calculated by taking off from the original dose and not the previous dose.

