**Table: Carboplatin dose modification based on platelet count**

Platelet count within 24 hrs. of therapy	Action to be taken
≥ 100,000	Treat at current dose
< 100,000	Hold treatment, and resume therapy at AUC of 1.0 at the next weekly therapy planned when platelets ≥ 100,000. If thrombocytopenia requiring further chemotherapy break occurs, carboplatin will be discontinued for the remainder of the therapy.

- Renal toxicity: Serum creatinine will be measured weekly within 24 hours of carboplatin dosing. If the serum creatinine has not changed more than 25% relative to the serum creatinine at baseline, the creatinine clearance and carboplatin dose need not to be recalculated. If there is a rise or fall greater than 25% relative to baseline serum creatinine values, then the creatinine clearance and carboplatin dose must be recalculated.

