## 11.0 MEASUREMENT OF EFFECT

### 11.1.1 Definitions

Evaluable for toxicity. All participants who go on to surgery will be evaluable for toxicity from the time of their first treatment. Patients who are screened will be evaluated and the reason for screen failure will be recorded

Evaluable for Primary Outcome: Only patients who are entered and have surgery will be eligible for assessment of the primary outcomes (LRC, PFS). All patients who have had surgery will be analyzed on an ITT for LRC, PFS, and survival.

Progression-Free Survival: Progression-Free Survival (PFS) is defined as the duration of time from start of treatment to time of objective disease progression or death.

Local Regional Control (LRC) will be defined as local and regional control of disease, censored for death.

Overall Survival (OAS) will be defined as alive at the time of analysis, this will be analyzed as for the entire trial, for all randomized patients and only for those patients randomized who received one dose of radiotherapy.

Post Recurrence LRC: Surveillance Patients who recur will be assessed for LRC post treatment for their initial recurrence

Post Recurrence PFS Surveillance Patients who recur will be assessed for PFS post treatment for their initial recurrence

Ultimate Disease Control will be defined as those patients who are alive and disease free at the time of analysis

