### **13.2 Procedures for AE and SAE Recording and Reporting**

Reporting: Participating investigators will assess the occurrence of AEs and SAEs at all participant evaluation time points during the study.

All AEs and SAEs whether reported by the participant, discovered during questioning, directly observed, or detected by physical examination, laboratory test or other means, will be recorded in the participant's medical record and on the appropriate study-specific case report forms.

The descriptions and grading scales found in the CTEP Active Version of the NCI Common Terminology Criteria for Adverse Events (CTCAE) will be utilized for AE reporting. The CTEP Active Version of the CTCAE is identified and located on the CTEP website at:

[http://ctep.cancer.gov/protocolDevelopment/electronic\\_applications/ctc.htm](http://ctep.cancer.gov/protocolDevelopment/electronic_applications/ctc.htm)

All appropriate treatment areas should have access to a copy of the CTEP Active Version of CTCAE.

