#### Reporting of Serious Adverse Events

All investigators NHLBI must report both expected (protocol defined) and unexpected serious adverse events. All serious adverse events must be reported directly to the clinical center's IRB within 10 working days of knowledge of the event, or as dictated by the specific IRB policy, whichever is sooner. All deaths and unexpected serious adverse events must be reported to the IRB within 24 hours of knowledge of the event, or as dictated by the specific IRB policy, whichever is sooner. The investigators will notify the study sponsor of any deaths and unexpected serious adverse events via e-mail within 24 hours of receipt of the event. These events will also be reported to the DSMB chair within 72 hours of notification. All serious adverse events will be reported to the DSMB at least semi-annually, at the discretion of the DSMB. In addition, the investigators are expected to comply with their institutional policies and reporting requirements.

After recruitment of half of the study subjects (100) a full dataset analysis will be performed by the investigators and the statistical support group to ensure that outcomes are comparable to current standards. This will include statistical analysis of adverse events, recurrence rates after surgical therapy, outcomes of adjuvant therapy arms, and disease specific survival. Deviation from the proposed recurrence rates or overall disease specific survival will result in halting the trial. The primary endpoints are DFS and LRC at 3 and 5 years. Kaplan-Meier curves will be estimated for the standard therapy and the experimental therapy groups. Ninety-percent one-sided confidence intervals will be calculated for DFS at 3 and 5 years in the surgical and surgical/adjuvant therapy groups. The secondary endpoint of overall survival will be analyzed using Kaplan-Meier curves and a log-rank test for the difference between the two therapy groups. Five year OAS, DFS and LRC will be calculated using a log-rank test will be used to test for differences between the two treatment groups. Toxicity is another secondary endpoint. We will compute for each arm the toxicity rate and provide the corresponding 90% confidence intervals based on the exact binomial distribution.

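### The adverse-event definition has no trigger for a change in study chemotherapy, so a symptom-free cytopenia that holds, cuts or stops it need not be recorded, and haematological toxicity in Groups IIIA and IIIB can be undercounted

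*Combined protocol and SAP*

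**What the plan says.** Section 13.1.1 first defines an adverse event broadly, as any undesirable sign, symptom, medical condition or experience that starts or worsens after study treatment begins, whether related or not. It then restricts laboratory and test findings: "Abnormal laboratory values or diagnostic test results constitute adverse events only if they induce clinical signs or symptoms or require treatment or further diagnostic tests".

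Section 7.1 says that the adverse events it lists will drive dose delays, dose modifications and expedited reporting. Its carboplatin list reads: "The major dose limiting toxicities observed with Carboplatin single agent are myelosuppression and renal toxicity".

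Section 7.2 acts on blood counts. The carboplatin platelet table says for low platelets: "Hold treatment, and resume therapy at AUC of 1.0 at the next weekly therapy planned when platelets" have recovered. The cisplatin thrombocytopenia table holds the drug below 100,000 and steps the dose to 80% and then 60% after nadirs below 50,000, with the note: "Please note that dose reduction percentage is calculated by taking off from the original dose and not the previous dose".

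Section 14.2 (under Reporting of Serious Adverse Events) and Section 16.5 make toxicity a secondary endpoint: "We will compute for each arm the toxicity rate and provide the corresponding 90% confidence intervals based on the exact binomial distribution". Section 11.1.1 sets the population: "All participants who go on to surgery will be evaluable for toxicity from the time of their first treatment".

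**The concern.** The laboratory sentence in 13.1.1 is a closed list: symptoms or signs, treatment, or further tests. A change in study chemotherapy is not on it. Section 7, by contrast, treats myelosuppression as an adverse event precisely because it changes chemotherapy. The two sections give different answers for the same patient, namely one with low counts and no symptoms whose drug is held, reduced or stopped.

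Toxicity per arm is a secondary endpoint, adverse events enter the half-accrual analysis in Section 14.2, and the DSMB reviews toxicity. Count-driven dose changes arise where chemotherapy is given, which is mainly Groups IIIA and IIIB. Any miscount therefore runs in one direction: it makes the de-intensified chemoradiotherapy groups look less toxic. Appendix 4 adds a second site that gives chemotherapy, so two sites could also apply an unclear rule differently.

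**Working it through.** The documents give no toxicity rate, no target rate and no size for Group III, so there is no stated figure to reproduce. The check is a comparison of rules, followed by an illustration.

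**Step 1. Test each laboratory-driven change in Section 7.2 against the three triggers in 13.1.1.**

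- *Carboplatin, ANC 1.0 to below 1.5:* the dose is cut to AUC 1.5. No hold, treatment or extra test is prescribed. No trigger is met. Section 7.2.1 adds that a reduced carboplatin dose is not raised again, so the effect lasts. This is the clearest case.
- *Carboplatin, ANC below 1.0:* hold, then resume at AUC 1.5; a further break stops the drug. Antibiotics and growth factors are mentioned only for febrile neutropenia. Without fever, the only possible trigger is the repeat count.
- *Carboplatin, platelets below 100,000:* hold, then resume at AUC 1.0; a further break stops the drug. Again only the repeat count could qualify.
- *Cisplatin, platelets:* hold below 100,000; 80% or 60% dose after nadirs below 50,000. Again only the repeat count could qualify.
- *Cisplatin, creatinine clearance below 60 mL/min:* hold, with extra hydration and weekly repeat creatinine. This is treatment and further testing, so the rule is met.
- *Hearing loss:* the decision to stop cisplatin involves formal hearing tests, and hearing loss is itself a sign or condition. The rule is met.

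Only symptom-free cytopenias remain.

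**Step 2. Is a recount a further diagnostic test?** Section 7.2.1 already requires minimum counts before chemotherapy, and the carboplatin tables use counts within 24 hours of dosing. A recount before the next weekly dose is thus arguably routine. It can be read either way.

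**Step 3. How far could a rate move?** Let *h* be the share of all patients in a group whose only countable toxicity is an uncounted cytopenia.

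- Any-toxicity rate: reported rate = true rate − *h*.
- Haematological rate: reported rate = true rate − (share with an uncounted cytopenia and no counted one). Other kinds of toxicity do not mask the loss.

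Exact 90% limits for x of n are the 0.05 quantile of Beta(x, n − x + 1) and the 0.95 quantile of Beta(x + 1, n − x). The inputs below (n = 30 and the true rates) are assumptions, not figures from the plan.

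- True any-toxicity 18/30 = 60% (43.4–75.0%).
- *h* = 0: unchanged at 60%.
- *h* = 10% (3 patients): 15/30 = 50% (33.9–66.1%).
- *h* = 20% (6 patients): 12/30 = 40% (25.0–56.6%).
- Near the ceiling, one patient lost: 28/30 = 93.3% becomes 27/30 = 90.0%, a fall of 3.3 points.

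The effect on an any-toxicity rate runs from zero up to *h*, and nothing in the documents fixes *h*.

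**The case against.** The strongest case is that other text already points to capture. Section 7.1 names myelosuppression under an adverse-event list. Section 13.2 covers events "directly observed, or detected by physical examination, laboratory test or other means, will be recorded in the participant's medical record", and for grading it says: "The descriptions and grading scales found in the CTEP Active Version of the NCI Common Terminology Criteria for Adverse Events (CTCAE) will be utilized". Section 13.1.2 gives blood dyscrasias as an example of a possible serious event. Section 14.1 requires a treatment form each cycle, and the DSMB may ask for laboratory values. Restricting symptom-free laboratory findings is also a legitimate design choice, and the carboplatin tables reach only patients moved off cisplatin.

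Part of this stands. It shows that the authors probably meant to record dose-limiting myelosuppression, and it narrows the population for the clearest case. It does not close the gap. Sections 13.2 and 13.1.2 apply to something that is already an adverse event, and the blood-dyscrasia example also requires jeopardy and intervention. Section 7.1 does not cure 13.1.1; it conflicts with it. A treatment form records the dose change but does not make the cytopenia an adverse event. The cisplatin platelet table applies without any drug switch.

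Three stronger readings are tempting and are not supported:

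- *That nephrotoxicity and ototoxicity also drop out.* Step 1 shows that they meet the rule.
- *That the toxicity rate is understated as a matter of fact.* Sections 14.2 and 16.5 give no grade, event list or numerator and never tie the rate to 13.1.1. Section 7.2.2 itself speaks of haematological toxicity, so the rate might include these events.
- *That grade 4 counts escape reporting under Section 13.4.1.* That section classifies events by grade and does not repeat the laboratory restriction, so this is only an inference.

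**Conclusion.** The point holds in limited form. Taken literally, 13.1.1 allows a symptom-free cytopenia that changes chemotherapy to go unrecorded as an adverse event, in conflict with Section 7. Haematological toxicity in Groups IIIA and IIIB can therefore be undercounted or recorded inconsistently, and this can carry into the per-arm toxicity rate and the DSMB review.

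The size cannot be derived. It depends on the number of chemoradiotherapy patients, the share with no other counted event, and how sites read the repeat-count question. For an any-toxicity rate it is zero if every such patient has another counted event, which is plausible under a definition that takes in any undesirable sign or symptom of any grade from surgery onward. A haematological rate is affected more directly.

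A reader might attach a figure of 5 to 20 points, by assuming 40 patients, 30–40% with another counted event, and a laboratory-only event in 10–30% of the rest. None of those inputs is in the documents, and the range leaves out zero, so it should not be used.

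**What to change.** Reconcile 13.1.1 with Section 7 by adding one trigger: a laboratory or test result is also an adverse event if it leads to a hold, reduction, substitution or discontinuation of study treatment under Section 7.2. This also settles the repeat-count ambiguity for these cases. State in Sections 14.2 and 16.5 that the toxicity rate uses this definition, and use it for the DSMB toxicity tables.

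The dosing rules already need these counts, so no new tests follow. The cost is a few more adverse-event entries and possibly a higher reported toxicity rate. No dosing rule changes. A further trigger based on CTCAE grade alone would be a matter of preference and is not needed to close this gap.

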#### 13.1.2 Serious Adverse Event (SAE)

A serious adverse event (SAE) is any adverse event, occurring at any dose and regardless of causality that:

- Results in death.

CONFIDENTIAL

This document is confidential. Do not disclose or use except as authorized.

- Is life-threatening. Life-threatening means that the person was at immediate risk of death from the reaction as it occurred, i.e., it does not include a reaction which hypothetically might have caused death had it occurred in a more severe form.
- Requires or prolongs inpatient hospitalization (i.e., the event required at least a 24-hour hospitalization or prolonged a hospitalization beyond the expected length of stay). Hospitalization admissions and/or surgical operations scheduled to occur during the study period, but planned prior to study entry are not considered SAEs if the illness or disease existed before the person was enrolled in the trial, provided that it did not deteriorate in an unexpected manner during the trial (e.g., surgery performed earlier than planned).
- Results in persistent or significant disability/incapacity. Disability is defined as a substantial disruption of a person's ability to conduct normal life functions.
- Is a congenital anomaly or birth defect; or
- Is an important medical event when, based upon appropriate medical judgment, it may jeopardize the participant and require medical or surgical intervention to prevent one of the outcomes listed above. Examples of such medical events include allergic bronchospasm requiring intensive treatment in an emergency room or at home; blood dyscrasias or convulsions that do not result in inpatient hospitalization, or the development of drug dependency or drug abuse.

Events **not** considered to be serious adverse events are hospitalizations for:

- Routine treatment or monitoring of the studied indication, not associated with any deterioration in condition, or for elective procedures.
- Elective or pre-planned treatment for a pre-existing condition that did not worsen.
- Emergency outpatient treatment for an event not fulfilling the serious criteria outlined above and not resulting in inpatient admission.
- Respite care.

### 13.1.3 Expectedness

Adverse events can be 'Expected' or 'Unexpected.'

#### 13.1.3.1 Expected adverse event

Expected adverse events are those that have been previously identified as resulting from administration of the agent. For the purposes of this study, an adverse event is considered expected when it appears in the current adverse event list, the Investigator's Brochure, the package insert or is included in the informed consent document as a potential risk.

Refer to Section 6.1 for a listing of expected adverse events associated with the study agent(s).

#### 13.1.3.2 Unexpected adverse event

For the purposes of this study, an adverse event is considered unexpected when it varies in nature, intensity or frequency from information provided in the current adverse event list, the Investigator's Brochure, the package insert or when it is not included in the informed consent document as a potential risk.

### 13.1.4. Attribution

Attribution is the relationship between an adverse event or serious adverse event and the study treatment. Attribution will be assigned as follows:

CONFIDENTIAL

This document is confidential. Do not disclose or use except as authorized.

- Definite – The AE is clearly related to the study treatment.
- Probable – The AE is likely related to the study treatment.
- Possible – The AE may be related to the study treatment.
- Unlikely – The AE is doubtfully related to the study treatment.
- Unrelated – The AE is clearly NOT related to the study treatment.

### **13.2 Procedures for AE and SAE Recording and Reporting**

Reporting: Participating investigators will assess the occurrence of AEs and SAEs at all participant evaluation time points during the study.

All AEs and SAEs whether reported by the participant, discovered during questioning, directly observed, or detected by physical examination, laboratory test or other means, will be recorded in the participant's medical record and on the appropriate study-specific case report forms.

The descriptions and grading scales found in the CTEP Active Version of the NCI Common Terminology Criteria for Adverse Events (CTCAE) will be utilized for AE reporting. The CTEP Active Version of the CTCAE is identified and located on the CTEP website at:

[http://ctep.cancer.gov/protocolDevelopment/electronic\\_applications/ctc.htm](http://ctep.cancer.gov/protocolDevelopment/electronic_applications/ctc.htm)

All appropriate treatment areas should have access to a copy of the CTEP Active Version of CTCAE.

### **13.3 Reporting Requirements**

Each participating investigator is required to abide by the reporting requirements set by the MSSM. The study must be conducted in compliance with FDA regulations, local safety reporting requirements, and reporting requirements of the principal investigator.

Each investigator will be responsible to report SAEs that occur at that institution to their respective IRB. It is the responsibility of each participating investigator to report serious adverse events to the study sponsor and/or others as described below.

### **13.4 Reporting to the Study Center**

#### **13.4.1 Serious Adverse Event Reporting**

All serious adverse events that occur after the initial dose of study treatment, during treatment, or within 30 days of the last dose of treatment must be reported to the MSSM Overall Principal Investigator on the local institutional SAE form for the local IRB and electronically on the eRAP CRF. This includes events meeting the criteria outlined in Section 11.1.2, as well as the following:

- Grade 2 (moderate) and Grade 3 (severe) events that are unexpected and at least possibly related/associated with the intervention.
- All Grade 4 (life-threatening or disabling) events that are unexpected or not specifically listed in the protocol as not requiring reporting.

CONFIDENTIAL

This document is confidential. Do not disclose or use except as authorized.

- All Grade 5 (fatal) events while the participant is enrolled and actively participating in the trial OR when the event occurs within 30 days of the last study intervention.

Note: If the participant is in long term follow up, report the death at the time of continuing review.

Participating investigators must report each serious adverse event to the MSSM Overall Principal Investigator within 24 hours of learning of the occurrence by Fax and email. In the event that the participating investigator does not become aware of the serious adverse event immediately (e.g., participant sought treatment elsewhere), the participating investigator is to report the event within 24 hours after learning of it and document the time of his or her first awareness of the adverse event. Report serious adverse events by telephone, email or facsimile to:

[name] at Ph- [contact]    [[contact]](mailto:[contact])

Within the following 24-48 hours, the participating investigator must provide follow-up information on the serious adverse event. Follow-up information should describe whether the event has resolved or continues, if and how the event was treated, and whether the participant will continue or discontinue study participation.

#### **13.4.2 Non-Serious Adverse Event Reporting**

Non-serious adverse events will be reported to the MSSM Overall Principal Investigator on the toxicity Case Report Forms.

#### **13.5 Reporting to the Institutional Review Board (IRB)**

Investigative sites within MSSM will report all serious adverse events directly to the MSSM Office for Human Research Studies

Other investigative sites should report serious adverse events to their respective IRB according to the local IRB's policies and procedures in reporting adverse events. A copy of the submitted institutional SAE form should be forwarded to:

[name] at Ph- [contact]    [[contact]](mailto:[contact])

The MSSM Principal Investigator will submit SAE reports from outside institutions to the MSSM Office for Human Research Studies according to MSSM IRB policies and procedures in reporting adverse events.

